10.0 Procedures Involved

10.1 Describe and explain the study design.

Once a subject has been identified, the initial visit will be scheduled. During the experimental day, informed consent will be completed, and the subjects will complete the following tasks: (1) an investigator will conduct visual acuity assessments of both eyes (Snellen). (2) The subjects will be asked to complete a survey (on contact lens satisfaction). (3) After the survey, the subject will sit with their lenses for assessment using the Keratograph topographer. (4) After topography, slit lamp assessment of the rigid lenses, and then of the cornea and conjunctiva (after lens removal) with and without Lissamine Green staining will be done.

At visit one, the following additional task will be performed: (1) The subject will be asked to sit for a corneal or scleral lens fitting visit (based on what they wear habitually), where the investigator will fit the subject with a commercially available scleral or corneal lens. All subjects will be refit into the Advanced Vision Technologies (AVT) brand of rigid lenses, manufactured at AVT Technologies in Colorado. If they already wear the AVT brand, the lens parameters will simply be re-ordered. All lenses will undergo a diagnostic fit with an AVT lens. The parameters available at AVT are similar to those available at all other major labs in the US.

A second visit will be to evaluate the fit of the ordered study lenses (which will have been coated with the HydraPEG coating), and will be for the dispense of the lenses. In addition to evaluating the lenses, the subjects will be asked to complete a short survey on their satisfaction with their current lenses. After this visit, the subjects will then wear the lenses for 30 days, on a daily basis as they habitually would, cleaning the lenses with ClearCare hydrogen peroxide cleaning system, a commonly used commercially available soft and rigid contact lens cleaner. After 30 days of lens wear, they will report for visit 3.

At the third visit, the same testing will be performed from visits 1 and 2, the subject will also be given an additional survey regarding the satisfaction with the HydraPEG lenses, and then the Tangible Boost kit or the placebo kit (consisting of

Page 9 of 22 Revised: July 24, 2017

two vials with Unique pH) solutions will be dispensed (randomized) to store their lenses in for 30 minutes that night.

The solution will be dispensed and the subjects trained on its use, and the subjects will be asked to store their lenses in the given solution for 30 minutes that evening, and then transfer their lenses to Unique pH multipurpose rigid lens solution for overnight storage. For the initial training with the Boost or placebo system, the users will undergo an approximately 60-minute user training in which there will be visual and audio recording and still photographs taken in order for a human factors company (Userwise) to analyze the usability of the product. The investigator at the study visit will act as the monitor for the training session. This recorded training step was specifically designed to allow for proper evaluation of the usability of the product, which they will report to the FDA to ensure usability. At the initial visit, the subject will have indicated on the informed consent form whether they agree to participate in the recorded portion of the training. If they do not participate in the recording, they can still be trained and participate in the study.

The subjects will report to the Ocular Surface Institute the next day for Visit 4, at which time the comfort and visit tests will occur again, and an additional survey to evaluate the boost treatment will be given. After visit 4, the subjects will continue to wear the study lenses daily for an additional 60 days, treating their lenses again in the Boost or placebo solution at the midpoint between visit 4 and 5 (30 days after the first treatment with Boost), otherwise cleaning nightly with ClearCare, and will then report to the clinic again 30 days after the midway treatment (approximately 90 days after the initial HydraPEG dispense). The same visit testing will be done at this final and 5th visit, and a final short survey will be done, and then the lenses will be collected from the subjects and sent back to Tangible Science, Inc. for their internal testing of the lenses (no involvement of the UH research team). At this time the study will conclude.

The following table outlines each of the study visits and tells what procedures will be done at each visit:

Procedure	Length of Time Required for	Frequency of Repetition
VISIT 1: Initial Evaluation		
Informed consent & HIPAA	35 minutes	Once
General History and medications	5 minutes	Once per visit
Visual Acuity	5 minutes	Once per visit

Page 10 of 22 Revised: July 24, 2017

Questionnaires (CLDEQ8 + VAS)	10 minutes	Once per visit
Keratograph Surface Evaluation	5 minutes	Once per visit
Slit-lamp Examination (with lenses	10 minutes	Once per visit
on and after lens removal)		
Scleral lens / corneal lens fitting	30 minutes	Once
	100	
TOTAL TIME	100 minutes	
VISIT 2: HydraPEG dispense		
Visual Acuity	5 minutes	Once per visit
Questionnaires (CLDEQ8 + VAS	10 minutes	Once per visit
+ Secondary VAS for V2)		Shee per visit
, , , , , , , , , , , , , , , , , , ,		
Keratograph Surface Evaluation	5 minutes	Once per visit
Slit-lamp Examination	5 minutes	Once per visit
Scleral/corneal lens evaluation &	20 minutes	Once
dispense. (handling & care		
paperwork will be dispensed at this		
visit)		
TOTAL TIME		
*additional visits may be required to		
not acceptable. It is anticipated that		
Visit 1 and 2). The only tasks done		
of the lens and make any necessary of		
minutes – for a slit lamp evaluation		
determined. Since these are establish	ned wearers, we do not antici	pate a long fitting process.
VISIT 3: Tangible Boost Dispense		T
Visual Acuity	5 minutes	Once per visit
Questionnaires (CLDEQ8 + VAS	10 minutes	Once per visit
+ Secondary VAS for V3)		
Keratograph Surface Evaluation	5 minutes	Once per visit
Slit-lamp Examination	5 minutes	Once per visit
Tangible Boost kit dispense &	60 minutes	Once
training		
TOTAL TIME	85 minutes	
VISIT 4: Tangible Boost Follow-U	p #1	
Visual Acuity	5 minutes	Once per visit
Questionnaires (CLDEQ8 + VAS	10 minutes	Once per visit
+ Secondary VAS for V4)		
Keratograph Surface Evaluation	5 minutes	Once per visit
Keratograph Surface Evaluation Slit-lamp Examination	5 minutes 5 minutes	Once per visit Once per visit

Page 11 of 22 Revised: July 24, 2017

FULL PROTOCOL TITLE: An Evaluation of Tangible Boost Replenishing System on the Continued Efficacy of Tangible HydraPEG Rigid Gas Permeable Contact Lens Coating.

TOTAL TIME	25 minutes	
VISIT 5		
Visual Acuity	5 minutes	Once per visit
Questionnaires (CLDEQ8 + VAS + Secondary VAS for V5)	10 minutes	Once per visit
Keratograph Surface Evaluation	5 minutes	Once per visit
Slit-lamp Examination	5 minutes	Once per visit
TOTAL TIME	25 minutes	

10.2 Provide a description of all research procedures being performed and when they are performed.

The testing descriptions are summarized in the table below:

Test	Description	Video/Audio recording
General History and Medications	Participants will be asked questions about their general, ocular and medication use histories along with contact lens use history if applicable.	No
Questionnaires	Subjects will be asked to fill out the following questionnaires: • Contact Lens Dry Eye Questionnaire - 8 (CLDEQ - 8) • Visual analog scale (VAS) 0-100 • Secondary VAS scales at Visits 2-5 (unique to each visit) These questionnaires assess the level of eye and/or contact lens discomfort, and assess the subject perception of their habitual lenses and the coated lenses before and after Boost treatment.	No

Page 12 of 22 Revised: July 24, 2017

FULL PROTOCOL TITLE: An Evaluation of Tangible Boost Replenishing System on the Continued Efficacy of Tangible HydraPEG Rigid Gas Permeable Contact Lens Coating.

0.1.1/0.1	TT1 ' '11 ("1 1 1 1 1 1 1	NT
Scleral/Corneal lens fitting	The examiner will fit the subjects with scleral or corneal contact lenses using commercially available lens fitting sets (AVT scleral and corneal designs, AVT Technologies, CO). The lenses will be fit using the customary fitting procedure, where a diagnostic lens is applied to the eye, an over-refraction is performed, and then customized lenses are ordered with the over-refraction incorporated and any fitting parameters are altered based on the investigators' expertise. Once the lenses are dispensed, the subjects will be reminded of proper handling and cleaning techniques, and given a handout on lens care. In addition, at the 30-day visit subjects will be given instructions on the tangible boost kit or placebo that they are supplied.	No
Scleral/Corneal	The ordered rigid lenses will be applied to the eye of the	No
Lens Evaluation	subject by the investigator, after which the fit and vision will be evaluated. At this time, if the fit of the lens is adequate, the lenses will be dispensed. If there are additional parameter changes needed, they will be ordered at this time.	
Visual Acuity	The participant's vision in each eye will be measured with a high contrast visual acuity chart for the subjects' habitual lenses and the test lenses. The participant will be asked to cover one eye and read the chart, and this procedure will be repeated for the other eye.	No
Slit-lamp	The participant's front portion of each eye and contact	No
Examination	lenses will be examined with a lighted microscope. The participant will be asked to place his/her chin on the chinrest and place his/her forehead against the bar and look straight ahead. The instruments light will be shined onto the eye to visualize the ocular surface for approximately 2-3 minutes per eye.	
Oculus	The OCULUS Keratograph® 5M is an advanced corneal	No
Keratograph	topographer with a built-in real keratometer and a color camera optimized for external imaging. It also has a module called the Non-invasive keratograph break-up time, which allows us to evaluate the wettability of the front surface of the lens. The new infrared illumination is not visible to the human eye. This prevents glare during the examination.	
Lissamine	Individual paper strips, impregnated with 1.5mg of Lissamine	No
GreenGlo Strips	Green dye. The dye is attracted to dead cells and irregularities at the ocular surface. These strips are commonly	

FULL PROTOCOL TITLE: An Evaluation of Tangible Boost Replenishing System on the Continued Efficacy of Tangible HydraPEG Rigid Gas Permeable Contact Lens Coating.

	used in practice as the gold standard for evaluating compromise to superficial corneal or conjunctival tissue. (for this study we will be not be using sodium fluoroecein, which is also sometimes used to assess the tear film).	
Product usability training	Because this is a new product, the company is interested in evaluating the usability of the product based on the instructions in the kits. The subjects will be asked to read the instructions and use the boost product on a pair of dummy lenses without any interference from the investigator. The investigator will act as the monitor, and they will follow the prompts on the instruction sheet (in the appendix) to lead the subjects through the training. The subjects will be recorded, and still photos may be taken. There are prompted questions that the investigator will ask the subjects about their use of the product (see the questions and prompts in the appendix document called Tangible Boost Datasheet). Subjects will be recognizable through the video and audio footage, because the company needs to evaluate facial expressions to observe usability characteristics. This will allow a human factors team at the company to assess how usable the product is based on the packaging and current instructions. See appendix for the Boost kit instructions, as well as the Userwise instruction and prompt sheet.	Yes

Statistical Analysis: Each individual will act as their own control to measure differences in pre and post contact lens measurements (paired non-parametric statistics), and this baseline data will be compared to normative data available for a soft contact lens wearing population. Descriptive statistics will also be employed to evaluate the overall response of the eye to a rigid lens with and without HydraPEG and with and without Tangible Boost.

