9.0 Study Endpoints

- 9.1 The primary endpoints in this study are as follows:
 - visual acuity
 - contact lens comfort questionnaire
 - keratograph surface evaluation (tear break up score)
 - ocular surface staining

Page 8 of 22 Revised: July 24, 2017

- 9.2 The secondary endpoints in this study are as follow:
 - contact lens fitting characteristics (apical clearance, limbal clearance, scleral landing evaluation)

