5.	Birthdate (mm/dd/yy):/				
6.	Gender: \square_1 Male \square_2 Female				
7.	Lens Indication:				
8.	Lens Type (circle one): Scleral	Corneal			
9.	Duration of lens wear (months/years):				
10.	Average # hours lens wear per week:				
11.	Hours of lens wear today:				
12.	CLDEQ-8 a. CLDEQ-8 completed and verified:	□₁ Yes	\square_2 No	CLDEQ-8 score:	
13.	VAS scale a. VAS scale completed and verified:	□ ₁ Yes	\square_2 No	VAS score:	
14.	Medications and Medical History a. Current medications or supplements?		□ ₁ Yes	\square_2 No	

UNIVERSITY of HOUSTON

15.

Diameter: ____ Lens Power:

Limbal Profile: _____

Landing Zone Profile: ______

Subject:	

_					
TH	IE OCULAR SURFACE INSTITUTE		Date:	/	/
	Evaluation of Tangible Boost F	Replenish	ing Syst	em	
c. d. e. f.	Was the concomitant medication log completed? Medical or ocular conditions? Was the medical and ocular history log completed? History of ocular surgeries, ocular injections or laser □₁ Yes □₂ No (If No, skip to question 10) Was the surgery more than 12 weeks ago? □₁ Yes Type of ocular surgery and when it occurred? /	\Box_1 Yes \Box_1 Yes procedures?	\square_2 No \square_2 No \square_3 N/A	ate:	/
Со	ntact lens history				
a.	Current lens brand				
00					
OS	·				
b.	Current lens parameters (if known)				
	Base curve:				
	SAG:				
	Diameter:				

c.	Did subject wear their own contact lenses 2 days prior to this appointment? \square_1 Yes \square_2	No

Visual Acuity with habitual lenses (logMAR): Record # of letters seen **16.**

OS: OD: _____

Over refraction (spherical only) **17.**

OD OS

Examiner Initials:

THE OCULAR SURFACE INSTITUTE

Sub	oject:		_
Date:	/	/	_

Evaluation of Tangible Boost Replenishing System

	OD			OS
		Movement		
		Centration		
		Apical Clearand	ce	
		Limbal Clearan	ce	
		Scleral Landing Z	one	
		Commonts		
Perform Kera	atograph NIBUT			
OD:	NIKf-BUT "until b	olink" (first break up)		
	NIKavg-BUT "unt	il blink" (average break up)		
	Level:			
	NIKf-BUT "25 sec	conds" (first break up)		
	NIKavg-BUT "25	seconds" (average break up))	
	Level:		7	
				
OS:	NIKf-BUT "until b	olink" (first break up)		
OS:	NIKf-BUT "until b NIKavg-BUT "unt	olink" (first break up) il blink" (average break up)		
OS:	NIKavg-BUT "unt	il blink" (average break up)		
OS:	NIKavg-BUT "unt Level:	il blink" (average break up) 		
OS:	NIKavg-BUT "unt Level:	il blink" (average break up) 		
OS:	NIKavg-BUT "unt Level: NIKf-BUT "25 sec	il blink" (average break up)		

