*Note evalua 7.	: Habitual lens fit does not need to tion. Slit lamp exam (after lens remov OD	be re-evaluated at this (al) Lids and lashes Conjunctiva Sclera	visit. They ma	oy be removed without

[figure not shown]

Subject:	

Date: _____/_____

Evaluation of Tangible Boost Replenishing System

TOTAL Score: OD _____ OS ____

- 9. Fitting with Study Lenses:
 - a. Visual Acuity with Study Lenses (logMAR): Record # of letters seen

OD: _____ OS: OD: ____

b. Over refraction

OD _____

c. Slit Lamp Evaluation of Study Lenses
OD

Movement
Centration
Apical Clearance
Limbal Clearance
Scleral Landing Zone
Comments

10. Comments and suggested changes to lens parameters:

11. Need for New Lens order? \square_1 Yes \square_2 No \square_3 Maybe

Examiner Initials: _____

OS

TUC	\cap	AD C	SIIDEVOE	INSTITUTE
		AK	DUKLWCE	HINDHIULE

Subje	ect:		
Date:	/	/	

Base curv	e:	
Diameter	·	
Lens Pow	er:	
Limbal Pr	ofile:	
Landing Z	one Profile:	
13. Keratograph 14. Perform Kera	•	are dispensable)? \square_1 Yes \square_2 No
OD:	NIKavg-BUT "until blink" Level: NIKf-BUT "25 seconds" (first break up)s" (average break up)
OS:	NIKavg-BUT "until blink" Level: NIKf-BUT "25 seconds" (first break up)s" (average break up)
15. Contact lens	order form filled out? \Box_1	Yes \square_2 No \square_3 Not Applicable
16. Gift card give	n? \square_1 Yes	\square_2 No
17. Dispensed Le	nses? \square_1 Yes	\square_2 No

THE OCULAR SURFACE INSTITU	ΠH

Subject:		
Date:	_/	/

18. Dispensed Unique pH?	\square_1 Yes	\square_2 No			
19. Dispensed DMV?	\square_1 Yes	\square_2 No			
20. Dispensed PuriLens?	\square_1 Yes	\square_2 No			
21. Lens Dispense log filled out?	□ ₁ Yes	□ ₂ No			
22. Follow up appt made (30 days and +1 day)? \square_1 Yes \square_2 No					
23. Follow up appt dates: Appt 4 date:					
Appt!	5 date:				

Subject:		
Date:	_/	/

Evaluation of Tangible Boost Replenishing System

VISIT 3

ours of Rigid lens wear today:			
urrent Cleaning solution:			·
urrently wearing study lenses?	\square_1 Yes \square_2	No	
CLDEQ-8 a. CLDEQ-8 completed and verified	d: □₁ Yes	\square_2 No	CLDEQ-8 score:
'AS scale . VAS scale completed and verifie	ed: □₁ Yes	\square_2 No	VAS score:
o. Extended VAS scale completed:	\square_1 Yes \square_1 Yes \square_1 Yes \square_1 Yes	\square_2 No \square_2 No	removal: vision:
Medications a. Any changes in medications? b. If yes, please specify:	□ ₁		No
Visual Acuity with Study Lenses (lo	gMAR): Record # of	letters seen	
OD: OS:			

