8.	Visual Acuity with Study Lenses (logMAR):	Record # of le	tters seen			
	OD: OS:					
9.	Over refraction (spherical only) OD OS					

Subject:	 	

Date:	/	/

Evaluation of Tangible Boost Replenishing System

	OD		OS
			
		_	
		_ Comments	
erform Ker	atograph NIBUT		
OD:	NIKf-BUT "until l	olink" (first break up)	
	NIKavg-BUT "un	til blink" (average break up)	
	Level:		
	NIKf-BUT "25 se	conds" (first break up)	
	NIKavg-BUT "25	seconds" (average break up)	
	Level:		
0.5	NUMER DESTRUCTION	1: 17/75 . 1	
OS:		olink" (first break up)	
	Level:	til blink" (average break up)	
		1.11.75	
	NIKt-BUT "25 sec	conds" (first break up)	
		seconds" (average break up)	
	Level:		
lit lamp exa	ım (after lens remo	oval)	
lit lamp exa	nm (after lens remo	oval)	os
-	-	oval) _ Lids and lashes	os
-	OD		os
-	OD	Lids and lashes	OS
-	OD	Lids and lashes Conjunctiva	OS
-	OD	Lids and lashes Conjunctiva Sclera	OS
-	OD	Lids and lashes Conjunctiva Sclera Cornea	OS

[figure not shown]

Subject:		
=		

[figure not shown]
Date: _____/_____

Evaluation of Tangible Boost Replenishing System

13. Corneal Fluorescein Staining (0-4 grading)

TOTAL Score: OD _____ OS ____

14. Are lenses still adequate to be worn? \square_1 Yes \square_2 No

If no, please indicated parameter changes indicated below:

- **15. Gift card given?** \square_1 Yes \square_2 No
- **16. Dispensed Unique pH?** \Box_1 Yes \Box_2 No
- **17. Dispensed DMV?** \square_1 Yes \square_2 No
- **18. Dispensed PuriLens?** \square_1 Yes \square_2 No
- **19. Follow up appt made (60 days)?** \square_1 Yes \square_2 No
- **20.** Call-log filled out for **30** days (reminder)? \square_1 Yes \square_2 No
- 21. Follow up appt date: _____

THE	OCIII	ΔD	SURFA	CF	INISTII	HITE
		\sim IX	SUKEA	W-E	HINDIH	UIL

Subject:		
Date:	/	/

VISIT 5

1.	Time of Day (military time) ::			
2.	Hours of Rigid lens wear today:			
3.	Current Cleaning solution:			
4.	Currently wearing study lenses? \square_1 Yes	\square_2 N	lo	
5.	CLDEQ-8 a. CLDEQ-8 completed and verified:	□₁ Yes	□ ₂ No	CLDEQ-8 score:
6.	VAS scale a. VAS scale completed and verified:	□ ₁ Yes	\square_2 No	VAS score:
	b. Extended VAS scale completed:	\square_1 Yes \square_1 Yes	\square_2 No \square_2 No \square_2 No \square_2 No	removal: vision:
7.	Medications a. Any changes in medications? b. If yes, please specify:	□ ₁ Y		
8.	Visual Acuity with Study Lenses (logMAR)	: Record # of lo	etters seen	
	OD: OS:			
9.	Over refraction (spherical only) OD OS			

Subject	:		
Date:	/	/_	

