 - **3** Frequently
 - 4 Constantly

When your eyes felt discomfort with your contact lenses, how intense was this feeling of discomfort...

b. At the end of your wearing time?

Never	Not at All				Very
have it	Intense				Intense
0	1	2	3	4	5

2. Questions about **EYE DRYNESS**:

- a. During a typical day in the past week while wearing your contact lenses, **how often** did your eyes feel dry?
 - 0 Never
 - 1 Rarely
 - 2 Sometimes
 - 3 Frequently
 - 4 Constantly

When your eyes felt dry, how intense was this feeling of dryness...

b. At the end of your wearing time?

Never	Not at All Intense				Very
have it					Intense
0	1	2	3	4	5

Patient	t/Sul	bject	#:	
Date:_	_/_	_/_	Time:	

3. Questions about CHANGEABLE, BLURRY VISION:

- a. During a typical day in the past week, **how often** did your vision change between clear and blurry or foggy while wearing your contact lenses?
 - 0 Never
 - 1 Rarely
 - 2 Sometimes
 - 3 Frequently
 - 4 Constantly

When your vision was blurry, how noticeable was the changeable, blurry, or foggy vision ...

b. At the end of your wearing time?

Never	ever Not at All ve it Intense				Very
have it					Intense
0	1	2	3	4	5

4. Question about CLOSING YOUR EYES:

During a typical day in the past week, how often did your eyes bother you so much that you wanted to close them?

- 0 Never
- 1 Rarely
- 2 Sometimes
- **3** Frequently
- 4 Constantly

5. Question about **REMOVING YOUR LENSES**:

How often during the past week, did your eyes bother you so much that you felt as if you needed to stop whatever you were doing and take out your contact lenses?

- 1 Never (please skip to question 14)
- 2 Less than once a week
- 3 Weekly
- 4 Several times a week
- 5 Daily
- 6 Several times a day

Date:
Study:
Subject #:
Visit #:
Eye: OD OS
Other Specifications:
Please rate on the scale below how comfortable your contact lenses feel at this moment.

extremely uncomfortable

extremely comfortable

Subject #:

Date:

Visit #:

Eye (circle): OD OS

4M	4M		4M		M/HC	
131	1.0	D	S	R	K	N
104	0.9	С	K	Z	0	Н
83	0.8	0	N	R	K	D
66	0.7	K	Z	V	D	С
52	0.6	V	S	Н	Z	0
42	0.5	Н	D	K	С	R
33	0.4	С	S	R	Н	N
26	0.3	S	V	Z	D	K
21	0.2	N	С	V	0	Z
16.5	0.1	R	Н	S	D	V
13	0.0	S	N	R	0	Н
10.5	-0.1	0	D	Н	K	R
8	-0.2	Z	K	С	S	N
6.5	-0.3	С	R	Н	D	V

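### Section 10.1 calls the primary visual acuity measure Snellen, but the worksheets use a logMAR letter count; the only score sheet supplied has one letter sequence, so learning could pass for improvement in the paired analysis.

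*Combined protocol and SAP*

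**What the plan says.** Section 9.1 introduces its list with "The primary endpoints in this study are as follows" and puts visual acuity first of four. It gives no scale, eye, time point or summary measure. Section 1.2 includes visual performance in the study hypothesis.

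The method of measurement is described in three places:

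- Section 10.1: "an investigator will conduct visual acuity assessments of both eyes (Snellen". It carries the same testing forward to Visits 3 and 5.
- Section 10.2, table of tests: a "high contrast visual acuity chart for the subjects' habitual lenses and the test lenses", one eye at a time, with no scale named.
- Visit worksheets in the appendix: "Visual Acuity with habitual lenses (logMAR): Record # of letters seen" at Visit 1 (item 16) and "Visual Acuity with Study Lenses (logMAR): Record # of letters seen" at Visit 2 (item 9a). The worksheets for Visits 3, 4 and 5 carry the same instruction.

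The acuity score sheet at the end of the appendix prints 14 rows of 5 letters, from 1.0 to -0.3 logMAR. It leaves the visit number blank and has the examiner mark "Eye (circle): OD OS". No second letter set and no rotation of charts is described.

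On analysis, section 10.2 says "Each individual will act as their own control to measure differences in pre and post contact lens measurements", using paired non-parametric statistics. Section 25.1 refers to differences between baseline and test data and lists several possible methods. Section 10.1 randomizes the Boost and placebo kits, but no section specifies a comparison of acuity between the arms.

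**The concern.** There are two linked problems. First, the protocol text and the data forms disagree on how a primary endpoint is measured, and section 9.1 does not settle it. The acuity variable to be analysed is therefore not fixed in advance.

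Second, if the supplied sheet represents the only chart, each eye reads letters that the other eye has just read, and both eyes meet them again at each visit. Visits 3 and 4 are one day apart and fall on either side of the first kit treatment. A paired pre/post test cannot separate a gain from knowing the letters from a gain due to the lens coating. At stake is a false finding of better vision after treatment.

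**Working it through.** The documents state no effect size, SD, power or significance level for acuity, so there is no plan figure to reproduce. The check has three parts.

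**1. The scale.** The sheet has 14 rows x 5 letters = 70 letters. Rows are 0.1 logMAR apart, so one letter is 0.1 / 5 = 0.02 logMAR, and logMAR = 1.10 - 0.02 x letters. Reading through the 0.0 row takes 11 rows x 5 = 55 letters: 1.10 - 0.02 x 55 = 0.00. All 70 letters give 1.10 - 0.02 x 70 = -0.30. The sheet therefore supports a letter score with an exact conversion. Nothing on the sheet or the worksheets calls for Snellen notation.

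**2. The number of readings.** The worksheets measure each eye at each visit: 2 eyes x 5 visits = 10 readings. Scleral wearers are also read with the diagnostic lens at Visit 1: 10 + 2 = 12. On the documents as supplied, all of these use the one printed sequence.

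**3. What a learning gain would do to a paired test.** Inputs:

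- n = 30, from section 5.2, with one acuity change per subject (assumed, since the plan does not say how the two eyes are combined)
- two-sided 0.05 level (assumed)
- true treatment effect zero
- gain of 1 to 3 letters (assumed), which is 0.02 to 0.06 logMAR
- SD of change of 3 to 6 letters (assumed)

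The rejection rate comes from the noncentral t distribution with 29 degrees of freedom and noncentrality (gain / SD) x sqrt(30). For a gain of 1 and SD of 4, that is 0.25 x 5.48 = 1.37.

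| Gain (letters) | SD 3 | SD 4 | SD 5 | SD 6 |
|---|---|---|---|---|
| 1 | 42% | 26% | 19% | 14% |
| 2 | 94% | 75% | 56% | 42% |
| 3 | 100% | 98% | 89% | 75% |

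A simulation of 4,000 trials at SD 4 gives similar rates for the signed-rank test: 25% for a 1-letter gain and 74% for a 2-letter gain. If the paired t-test were run within one arm of 15 (equal allocation assumed), the rates at SD 4 would be 15% and 44%.

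In the same simulation, a two-sample t-test of change between arms of 15 and 15, with the same gain in both, rejects in 4.3% (1 letter) and 4.6% (2 letters) of trials. That is close to the nominal 5%. A common gain therefore biases the paired comparison and cancels in the between-arm one.

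**The case against.** The strongest reply is that the conflict comes down to one word. The five worksheets agree with each other and with the score sheet, the section 10.2 wording is compatible with them, and no form has a Snellen field. The logMAR label most naturally names the chart, and the words after it say what to record. This is fair, and it disposes of three inferences that a reader might draw:

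- *Snellen lines and letter scores will be pooled.* That needs some examiners to follow section 10.1 and ignore the form.
- *The sign of change will be reversed* because letters rise and logMAR falls as vision improves. That needs whole counts up to 70 to be confused with decimals between -0.3 and 1.1.
- *Rounding to whole lines will add error.* No document calls for line-only scoring, and the worksheets ask for letters.

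The second reply is that one blank form does not prove one chart. Other appendix items that the protocol mentions are absent from the supplied text, and the sheet's header is garbled, so a version label could have been lost. This also stands in part: repeated use of the same letters is inferred from the only sheet supplied and from the silence on rotation. It is not stated.

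Third, the size of any gain is unknown. A reader might infer that learning is greatest from Visit 3 to Visit 4, or that scores will reach a ceiling. The documents support neither. Each eye has already been tested at three visits by the end of Visit 3, so learning could have levelled off. No baseline acuity is given, and a gain of 1 to 3 letters reaches 70 only from 67 or more.

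Fourth, randomization deals with a gain common to both arms, and section 25.1 allows methods that could compare them. That is correct, but the plan does not commit to such a comparison, and the analysis that it does describe is the exposed one.

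**Conclusion.** The point holds in a limited form. The conflict between Snellen in section 10.1 and a logMAR letter count on the forms is plain in the text, concerns a primary endpoint, and is not resolved by section 9.1. Repeated reading of one letter sequence, at least 10 times per subject, is what the documents describe as supplied, subject to the inference noted above. Any learning gain would then enter the stated paired analysis as improvement.

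The size of that bias cannot be taken from the documents. Under the assumed gains of 1 to 3 letters and SDs of 3 to 6 letters, false rejection ranges from 14% to nearly 100%. These rates illustrate sensitivity and are not a forecast. A Boost-versus-placebo comparison of change would largely remove the bias, but it is not specified. The matter should be corrected before data collection, because letters already learned cannot be unlearned at the analysis stage. It does not in itself invalidate the trial.

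**What to change.** 1. In section 10.1, delete the parenthetical reference to Snellen. In sections 9.1 and 10.2, define the endpoint as the number of letters read (0 to 70) on the attached logMAR chart, with one stated conversion: logMAR = 1.10 - 0.02 x letters.
2. Use different letter versions for right and left eyes and between visits, at least between Visits 3 and 4. Keep the order the same in both arms, and supply a matching score sheet for each version.

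The cost is some wording edits, the alternate charts and their score sheets; no visits are added. The downside is slight noise from differences in difficulty between versions. With a common order, such a difference cancels between arms but stays in a paired comparison, so the versions should be matched for difficulty. Rotation reduces the learning gain; it does not replace a specified comparison between the randomized arms.
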